IRT	interactive response technology
ITT	intent-to-treat
IXRS	Interactive Voice/Web Response System
LDH	lactate dehydrogenase
LMCI	late mild cognitive impairment
LTE	long-term extension
LOCF	last observation carried forward
MCI	mild cognitive impairment
MCMC	Markov chain Monte Carlo
MedDRA	Medical Dictionary for Regulatory Activities
MMRM	mixed-model repeated measures
MMSE	Mini-Mental State Examination
MOCA	Montreal Cognitive Assessment
mPDQ-20	Perceived Deficits Questionnaire-20 modified version
MRI	magnetic resonance imaging
NIA-AA	National Institute on Aging-Alzheimer's Association
NPI-10	Neuropsychiatric Inventory-10
PCS	potentially clinically significant
PET	positron emission tomography
pH	potential of hydrogen
PI	Principal Investigator
PK	pharmacokinetic(s)
PMM	pattern mixture model
PP	per-protocol
RBANS	Repeatable Battery for Assessment of Neuropsychological Status
ROI	region of interest
SAE	serious adverse event
SAP	statistical analysis plan
SD	standard deviation
SUSAR	suspected unexpected serious adverse reaction
SUVR	standard uptake value ratio
TEAE	treatment-emergent adverse event
██████	████████████████████
ULN	upper limit of normal
US	United States
WHO	World Health Organization

CONFIDENTIAL

The information contained herein may not be used, disclosed, or published without the written consent of Biogen MA Inc.

1 DESCRIPTION OF OBJECTIVES AND ENDPOINTS

1.1 Primary Objective and Endpoint

The primary objective of this study is to evaluate the efficacy of monthly doses of aducanumab in slowing cognitive and functional impairment as measured by changes in the Clinical Dementia Rating-Sum of Boxes (CDR-SB) score as compared with placebo in subjects with early Alzheimer's Disease (AD).

The primary endpoint that relates to this objective is change from baseline in CDR-SB score at Week 78.

1.2 Secondary Objectives and Endpoints

The secondary objectives of this study are:

- To assess the effect of monthly doses of aducanumab as compared with placebo on clinical progression as measured by the Mini-Mental State Examination (MMSE).
- To assess the effect of monthly doses of aducanumab as compared with placebo on clinical progression as measured by Alzheimer's Disease Assessment Scale-Cognitive Subscales (13 items) [ADAS-Cog 13].
- To assess the effect of monthly doses of aducanumab as compared with placebo on clinical progression as measured by Alzheimer's Disease Cooperative Study-Activities of Daily Living Inventory (Mild Cognitive Impairment version) [ADCS-ADL-MCI].

The secondary endpoints are:

- Change from baseline in MMSE score at Week 78.
- Change from baseline in ADAS-Cog 13 score at Week 78.
- Change from baseline in ADCS-ADL-MCI score at Week 78.

1.3 Tertiary Objectives and Endpoints

1.3.1 Tertiary Objectives

Safety and Tolerability

- To assess the safety and tolerability of monthly doses of aducanumab.
- To assess the immunogenicity of aducanumab.

Biomarker/Efficacy/Quality of Life

CONFIDENTIAL

The information contained herein may not be used, disclosed, or published without the written consent of Biogen MA Inc.

- To assess the effect of aducanumab on cerebral amyloid plaque content as measured by amyloid positron emission tomography (PET) imaging (in a subset of approximately 400 subjects).
- To assess the effect of aducanumab on behavior as measured by the Neuropsychiatric Inventory-10 (NPI-10).
- To assess the effect of aducanumab on subject health status, measured by EuroQol health status measures (EQ-5D [informant-rated and subject self-reported]).
- To assess the effect of aducanumab on subject self-reported cognitive function, measured by the modified Perceived Deficits Questionnaire-20 (mPDQ-20).
- To assess the correlation between primary endpoint and cerebral amyloid plaque content as measured by PET imaging.

Pharmacokinetics

- To collect and characterize the pharmacokinetic (PK) parameters of aducanumab in serum

1.3.2 Tertiary Endpoints

Safety and Tolerability

- Incidence of all adverse events (AEs) and serious adverse events (SAEs).
- Brain magnetic resonance imaging (MRI) findings including incidence of amyloid related imaging abnormality-edema (ARIA-E) and amyloid related imaging abnormality-hemorrhage or superficial siderosis (ARIA-H).
- Clinical laboratory shifts in reported values.
- Clinically significant changes in vital sign measurements and electrocardiograms (ECGs).
- Incidence of anti-aducanumab antibodies in serum.

Biomarkers/Efficacy/Quality of Life

- Change from baseline in amyloid PET signal at Week 26 (in a subset of sites and subjects).
- Change from baseline in amyloid PET signal at Week 78 (in a subset of sites and subjects).
- Change from baseline in NPI-10 score at Week 78.
- Change from baseline in subject-self-reported EQ-5D index score at Week 78.
- Change from baseline in informant-rated subject EQ-5D index score at Week 78.
- Change from baseline in mPDQ-20 at Week 78.
- Correlation between the primary endpoint and cerebral amyloid plaque content as measured by PET imaging over time.

Pharmacokinetics:

CONFIDENTIAL

The information contained herein may not be used, disclosed, or published without the written consent of Biogen MA Inc.

- Serum concentrations and PK parameters of aducanumab.

1.4 Additional Exploratory Objectives and Endpoints

1.4.1 Additional Exploratory Objectives

[REDACTED]

- [REDACTED]
- [REDACTED]
- [REDACTED]
- [REDACTED]
- [REDACTED]
- [REDACTED]
- [REDACTED]

[REDACTED]

- [REDACTED]
- [REDACTED]

1.4.2 Additional Exploratory Endpoints

[REDACTED]

- [REDACTED]
- [REDACTED]
- [REDACTED]
- [REDACTED]
- [REDACTED]
- [REDACTED]

CONFIDENTIAL

- [REDACTED]
- [REDACTED]

2 STUDY DESIGN

2.1 Study Overview

Study 221AD302 (EMERGE) is a multicenter, randomized, double-blind, placebo-controlled, parallel-group study in subjects with early AD, including mild cognitive impairment (MCI) due to AD and a subset of mild AD, followed by an optional dose-blinded long-term extension (LTE) period of up to 5 years. Approximately 1605 subjects will be enrolled across approximately 150 centers globally. The primary study objective is to evaluate the efficacy of monthly doses of aducanumab on the CDR-SB relative to placebo. Secondary objectives include assessment of the effect of monthly doses of aducanumab on clinical progression as compared to placebo. The safety of monthly doses of aducanumab will also be evaluated.

Table 1: Dosing Scheme for Aducanumab by Treatment Group and ApoE ε4 Carrier Status: Placebo-Controlled Period

Dose (every 4 weeks)		1	2	3	4	5	6	7 to 20
Treatment Group	Treatment Group Stratified by ApoE Status ²	Dose (mg/kg)						
High Dose	High Dose - ApoE ε4 (+)	1	1	3	3	6	6	10 ¹
	High Dose - ApoE ε4 (-)	1	1	3	3	6	6	10
Low Dose	Low Dose - ApoE ε4 (+)	1	1	3	3	3	3	3
	Low Dose - ApoE ε4 (-)	1	1	3	3	3	3	6
Placebo	Placebo - ApoE ε4 (+)	saline						
	Placebo - ApoE ε4 (-)	saline						

¹ 10 mg/kg is the target dose for all ApoE ε4 carriers assigned to the aducanumab high-dose group. Subjects enrolled under protocol versions 1-3 and assigned to the previous high-dose of 6 mg/kg will be titrated to 10 mg/kg upon receipt of at least 2 doses at 6 mg/kg.

² ApoE ε4 status recorded in the Interactive Voice/Web Response System (IXRS).

Subjects will be randomized in a 1:1:1 ratio to 1 of the 3 treatment groups: aducanumab high dose, aducanumab low dose and placebo, with stratification based upon their apolipoprotein E4 (ApoE ε4) carrier status (carrier/non-carrier) and site. During the placebo-controlled period, subjects will receive infusions of aducanumab or placebo approximately every 4 weeks for approximately 18 months (a total of 20 doses). Dose levels may be different in the same treatment group based upon subjects' ApoE ε4 carrier status, and specifically, ApoE ε4

carriers will receive placebo, aducanumab 3 mg/kg, or aducanumab 10 mg/kg whereas ApoE ϵ 4 non-carriers will receive placebo, aducanumab 6 mg/kg, or aducanumab 10 mg/kg. Aducanumab will be titrated for up to 6 doses prior to reaching the target dose as shown in Table 1 and Figure 1. Note: As of Protocol Version 4, 10 mg/kg is the target dose for all ApoE ϵ 4 carriers in the high-dose group. ApoE ϵ 4 carriers who were randomized to the high dose group when the target dose was 6 mg/kg (under protocol versions prior to Version 4) must have received 2 or more doses at 6 mg/kg prior to being titrated up to 10 mg/kg.

At the end of the double-blind, placebo-controlled treatment period, subjects who meet the extension entry criteria may enter a long-term safety and efficacy extension period, with all subjects receiving aducanumab approximately every 4 weeks (up to a total of 65 doses over 5 years). The treatment group for the LTE period will be assigned at the same time as the randomization for the placebo-controlled period, regardless of whether a subject entering the LTE period or not. Subjects who are assigned to the placebo group during the placebo-controlled period will be assigned to 1 of 2 active treatment groups in a 1:1 ratio (aducanumab low dose: aducanumab high dose) and randomization will be stratified by their ApoE ϵ 4 carrier status; for those who enter the LTE period, aducanumab will be titrated for up to 6 doses prior to reaching the target dose following the same schedule described for the placebo-controlled period. Subjects who are assigned to either aducanumab low dose or aducanumab high dose group in the placebo-controlled period will continue in the same treatment group for the LTE period; those who enter the LTE period will maintain the dosing scheme outlined in the protocol at the time of transition from the placebo-controlled period to the LTE period (e.g. subjects who are on stable dosing in the placebo-controlled period will continue on the same dose, subjects who are on a titration regimen during the transition will continue to titrate into the LTE period, and ApoE ϵ 4 carrier subjects who are enrolled in the LTE and randomized to the high-dose group prior to implementation of version 4 of the protocol will be allowed to titrate to 10 mg/kg).

[figure not shown]
Individual dose adjustments may be implemented in subjects who develop amyloid related imaging abnormalities (ARIA). See Protocol Section 7.2.1.

The total duration of study participation for each subject only participating in the placebo-controlled period of the study will be up to approximately 102 weeks, including a series of Screening visits within 8 weeks before administration of the first dose, a 76-week placebo-controlled treatment period, and a safety follow-up (FU) period of approximately 18 weeks after the final dose. The total duration of study participation for each subject participating in the placebo-controlled period and the LTE period will vary and be up to approximately 362 weeks, including a series of Screening visits within 8 weeks before administration of the first dose, a 76-week placebo-controlled treatment period, a 4-week FU period, a 256-week aducanumab dose-blind treatment period, and a safety FU period of approximately 18 weeks after the final dose.

Investigators, study site staff (except for the designated unblinded pharmacist/technician), and study subjects will be blinded to the subjects' randomized treatment assignment for the placebo-controlled period. During the LTE period, investigators and subjects will remain blinded to the treatment assignment in the placebo-controlled period and the aducanumab dose for the LTE period.

2.2 Study Schematic

Figure 1: Study Design

ApoE ε4 +/- = apolipoprotein E4 positive/negative; FU = follow-up; P = placebo; R = randomization date.

*Subjects who are assigned to placebo during the placebo-controlled period are randomized in a 1:1 ratio to high and low dose aducanumab treatment (stratified by their ApoE ε4 carrier status) for the long-term extension period on Study Day 1.

CONFIDENTIAL

The information contained herein may not be used, disclosed, or published without the written consent of Biogen MA Inc.

2.3 Schedule of Events

See Protocol Section 4.2.

3 SAMPLE SIZE JUSTIFICATION

The study's sample size is based, in part, on results from a protocol-specified interim analysis from Study 221AD103 which included 1 year data from 1, 3 and 10 mg/kg treatment groups.

A sample size of 450 subjects per treatment group (1350 in total) was planned to have approximately 90% power to detect a true mean difference of 0.5 in change from baseline CDR-SB at Week 78 between the 2 treatment groups. This power calculation was based on a 2-sided t-test assuming equal variance with a final significance level of 0.05, a standard deviation (SD) of 1.92 and a drop-out rate of 30%. The SD estimate of 1.92 for Week 78 reflected a 39% increase over the SD from the protocol-specified interim analysis of 1-year data.

The assumed true mean difference of 0.5 between the 2 treatment groups represents an approximately 25% reduction in the placebo mean change from baseline at Week 78 if the placebo mean change is estimated to be 2.

As defined in the protocol, the sample size for this study (and for the identically designed Study 221AD301) was reassessed in a blinded manner in November 2017 (approximately 3 months before enrollment completion and with about 10.6% of the data available on the primary endpoint from Studies 221AD301 and 221AD302 combined). At this timepoint, the SD of the primary endpoint was estimated based on the pooled blinded data from two studies using a modified version of Gould-Shih simple-adjustment one sample variance (Zucker et al. 1999):

$$s_{adj}^2 = s_{os}^2 - \frac{2N}{9(N-1)} \delta^2,$$

where N denotes the number of subjects included in the analysis for blinded sample size re-estimation (subjects with both baseline and Week 78 CDR-SB available at the time of sample size re-estimation), δ is the assumed true treatment effect (same treatment effect assumed for both the high dose group and low dose group in this analysis), and s_{os}^2 is the unadjusted one sample variance of the primary endpoint estimate from the pooled blinded data.

As a result of this analysis, the sample size has been increased from 1350 to 1605 (450 to 535 per treatment group) to assure adequate power for detecting a mean treatment effect of 0.5.

4 STATISTICAL ANALYSIS METHODS

4.1 General Considerations

This statistical analysis plan (SAP) only covers the analyses for the primary, secondary and tertiary objectives for the placebo-controlled portion of the study. Hereafter, the placebo-controlled portion of the study will be referred to as “the study” in the rest of this SAP (e.g.,

CONFIDENTIAL

The information contained herein may not be used, disclosed, or published without the written consent of Biogen MA Inc.

	Statistical Analysis Plan Placebo-Controlled Period	Final V1.0
---	---	-------------------

completion of the study means completion of the placebo-controlled portion). A separate SAP will be prepared for the analyses of the LTE period and integrated analyses across both portions of the study. The analyses of additional exploratory endpoints will be documented separately.

Summary tables will be presented using descriptive summary statistics. For continuous variables, summary statistics will generally include: number of subjects with data, mean, standard deviation, median, 25% percentile, 75% percentile, minimum and maximum. For categorical variables, this will generally include: number of subjects randomized or dosed, number with data, and the percent of those with data in each category.

There are two types of analysis displays for tables: by treatment group (analysis display A in Appendix 6.1) and by treatment group stratified by ApoE status (analysis display B in Appendix 6.1; here ApoE status refers to the status recorded in IXRS [see Table 1 for correspondence between treatment groups and treatment groups stratified by ApoE status]). The analysis display for each analysis will be defined in each section. All the listings will be presented by treatment group stratified by ApoE status, unless otherwise specified.

Unless otherwise specified, baseline value is defined as the most recent non-missing measurement collected prior to the first dose. Change from baseline will be defined as post-baseline value minus baseline value.

Unless stated otherwise, all statistical tests will be 2-sided with statistical significance level of 0.05.

The statistical software, SAS® will be used for all summaries and analyses.

4.1.1 Analysis Population

- Intent-to-treat (ITT) population:
The Intent-to-treat population is defined as all randomized subjects who received at least one dose of study treatment (aducanumab or placebo).
- Per-protocol (PP) population:
The per-protocol population is defined as all subjects in the ITT population and also
 - had no violations of the following inclusion criteria:
 - Must have at least 6 years of education or work experience to exclude mental deficits other than MCI or mild AD;
 - Must have a positive amyloid PET scan;
 - Must have:
 - A CDR-Global Score of 0.5;
 - A Repeatable Battery for Assessment of Neuropsychological Status (RBANS) score of 85 or lower indicative of objective cognitive impairment (based upon the Delayed Memory Index score);
 - An MMSE score between 24 and 30 (inclusive).
 - had at least 14 infusions.
 - did not make any change to concomitant AD symptomatic medications during the study.

CONFIDENTIAL

The information contained herein may not be used, disclosed, or published without the written consent of Biogen MA Inc.

- **¹⁸F-florbetapir amyloid PET analysis population:**
The ¹⁸F-florbetapir amyloid PET analysis population is defined as all randomized subjects who received at least one dose of study treatment (aducanumab or placebo), used ¹⁸F-florbetapir ligand for amyloid PET scan, and had an evaluable baseline amyloid PET SUVR value for the composite region-of-interest using cerebellum as the reference region.
- **¹⁸F-flutemetamol amyloid PET analysis population (applicable only to Japan):**
The ¹⁸F-flutemetamol amyloid PET analysis population is defined as all randomized subjects who received at least one dose of study treatment (aducanumab or placebo), used ¹⁸F-flutemetamol ligand for amyloid PET scan, and had an evaluable baseline amyloid PET SUVR value for the composite region-of-interest using cerebellum as the reference region.
- **Safety population:**
The safety population is defined as all randomized subjects who received at least one dose of study treatment (aducanumab or placebo). It is the same population as the ITT population.
- **Safety MRI population:**
The safety MRI population is defined as all randomized subjects who received at least one dose of study treatment (aducanumab or placebo) and had at least one post-baseline MRI assessment.
- **PK analysis population:**
The PK analysis population is defined as all randomized subjects who received at least one dose of study treatment (aducanumab or placebo) and had at least one measurable aducanumab concentration in serum.
- **Immunogenicity population:**
The analysis population for immunogenicity is defined as all randomized subjects who received at least one dose of study treatment (aducanumab or placebo) and had at least one post-dose sample evaluable for immunogenicity.

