4.5 Safety Analysis

4.5.1 General Considerations

Analysis population

Safety population will be used for safety analyses of AEs, clinical laboratory data, Columbia Suicide Severity Rating Scale (C-SSRS) data, ECG data and vital sign data (all the safety data except for ARIA data). Safety MRI population will be used for analyses of ARIA data.

Safety treatment groups

Different from the randomization treatment groups, if a subject who was randomized to placebo group accidentally received one or more doses of the active treatment during the study, he/she will be classified as either low or high dose group for all the safety analyses, depending on the ApoE status and the maximal dose level of the active treatment received (Table 5). A listing of such subjects will be provided, as described in section 4.2.5. Safety treatment groups will be the same as the randomization treatment groups for other subjects (subjects randomized to active treatment groups, and subjects randomized to placebo without any accidental active dose). Safety treatment groups will be used for all the safety analyses unless otherwise specified.

Table 5: Safety treatment groups for placebo subjects with accidental active treatment

Randomization treatment group	Randomization ApoE status	Safety treatment group classification based on the maximum dose level of the accidental active treatment		
		>0 to 3 mg/kg	>3 to 6 mg/kg	>6 mg/kg
Placebo	ApoE ε4 (+)	Low dose	High dose	High dose
	ApoE ε4 (-)	Low dose	Low dose	High dose

Safety analysis displays

AEs, clinical laboratory data, C-SSRS data, ECG data and vital sign data (all the safety data except for ARIA data) will be summarized by treatment group (placebo, low dose, high dose and BIIB037 total; analysis display A in Appendix 6.1), unless otherwise specified. All the ARIA related tables will be presented by treatment group stratified by ApoE status (3 columns under each treatment group: ApoE ε4+, ApoE ε4- and total; analysis display B in Appendix 6.1), unless otherwise specified. A subset of AE tables will also be presented by treatment group stratified by ApoE status in addition to by treatment group. All the listings will be presented by treatment group stratified by ApoE status.

Incidence, incidence proportion and incidence rate

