6.2 Protocol Deviation Classification

Deviation Category	Deviation Description	Severity Classification
Administrative criteria	Study team member performing study assessments without being authorized as per delegation log.	Minor
Administrative criteria	Unblinded information made available to the blinded CRA.	Major
Administrative criteria	Unblinded information made available to the blinded site personnel.	Major
Administrative criteria	Incorrect version of any assessments used	case by case
Administrative criteria	Filing issues misfiling of documents	N/A
Administrative criteria	Correction of source data not compliant with GCP	N/A
Administrative criteria	Sharing of account credentials between raters on the MedAvante Virgil tablet/Portal, or sharing of accounts on any study system	Major
Concomitant Medications	Administration of any vaccination/booster should be given < 10 days prior to any dosing visit or 10 days after a dosing visit.	Minor
Concomitant Medications	Administration of any disallowed concomitant therapy to the subject.	Major
Concomitant Medications	Change of medications that subjects were receiving at enrollment or start of new medications or herbal preparations during the study period, without consultation with the investigator and review with the Medical Monitor	Case by case basis
Concomitant Medications	Change in AD medications during course of the study.	Minor
Eligibility and Entry criteria	Any "no" response to inclusion criteria and/or any "yes" response to exclusion criteria and subject was subsequently randomized for criteria.	Major
Eligibility and Entry criteria	Any eligibility assessment not performed.	Major
Eligibility and Entry criteria	Any eligibility assessment performed after the randomization of the patient (including lab samples), and subject is ineligible based upon assessment.	Major
Eligibility and Entry Criteria	Exclusionary lab value results but subject was dosed.	Major
Eligibility and Entry criteria	Subject not eligible based on scores of CDR, MMSE, RBANS DMI, as defined by inclusion criterion #6.	Major
Eligibility and Entry criteria	Subject on allowed chronic medications that have not been stable for at least 4 weeks prior to Screening V1 or use of AD medications at doses that have not been stable for at least 8 weeks prior to Screening V1.	Major

CONFIDENTIAL

The information contained herein may not be used, disclosed, or published without the written consent of Biogen MA Inc.

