Investigational Product Compliance	Incorrect cohort IP dispensed to subject	Major
Investigational Product Compliance	IP is not stored in blinded manner.	Major
Investigational Product Compliance	Unblinded pharmacist discarded/destroyed used IP vial prior to IP accountability being conducted by unblinded CRA and without previous approval.	case by case basis
Investigational Product Compliance	IP temperature log is not being maintained nor checked by the unblinded pharmacist.	Major
Investigational Product Compliance	Non-compliant with IP usage according to DHA (note: this does not include deviation regarding removing overfill on saline bag)	Major
Investigational Product Compliance	Dosing based on weight calculation is inaccurate (i.e., discrepancies between Weight Communication Form and IXRS entry, ratio not respected when preparing dose, etc.)	Major
Investigational Product Compliance	Overdose of IP occurs.	Major
Investigational Product Compliance	Overdose Form not faxed to Quintiles Lifecycle Safety within 24 hours of site being made aware of an overdose.	Major
Investigational Product Compliance	Titration schedule not respected when dosing subject.	Major
Investigational Product Compliance	Down-dosing / discontinuation of dosing not respected by the unblinded pharmacist following ARIA-H and ARIA-E cases, as prescribed by the protocol, investigator, Medical Monitor, and/or sponsor.	Major

CONFIDENTIAL

The information contained herein may not be used, disclosed, or published without the written consent of Biogen MA Inc.

	Statistical Analysis Plan Placebo-Controlled Period	Final V1.0
---	--	-------------------

Investigational Product Compliance	Missed infusion visit (not due to temporary discontinuation of dosing as prescribed by the protocol, investigator, Medical Monitor, and/or sponsor due to ARIA-H or ARIA-E case).	case by casis
Investigational Product Compliance	IP storage temperature out of range (2-8 °C).	Minor
Investigational Product Compliance	Administration of expired IP.	Major
Investigational Product Compliance	IP rounding discrepancies not in accordance with the Directions for Handling & Administration document (DHA).	Minor
Investigational Product Compliance	Administration of IP that was rejected after a temperature excursion.	Major
Investigational Product Compliance	IP administered in less than 21 days.	Minor
Laboratory assessments criteria	Ambient samples received at central laboratory that should have been shipped frozen.	Minor

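### The per-protocol population sets no condition on the treatment actually received, and none on AD-medication stability at entry

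*SAP*

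**What the plan says.** Section 4.1.1 gives three conditions beyond ITT membership. The subject "had no violations of the following inclusion criteria" (education or work experience; positive amyloid PET; the CDR, RBANS and MMSE entry scores), "had at least 14 infusions", and "did not make any change to concomitant AD symptomatic medications during the study". Nothing else removes a subject. Section 4.2.5 counts infusions of either aducanumab or placebo, so the infusion condition does not depend on the product.

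Section 4.3.1 groups all efficacy analyses per randomization. Section 4.3.2.3.2 applies the primary MMRM to the per-protocol population, and Table 2 lists this as supplementary for CDR-SB, MMSE, ADAS-Cog 13 and ADCS-ADL-MCI.

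The SAP foresees treatment errors elsewhere. For safety, section 4.5.1 and Table 5 move a subject to the low- or high-dose group "if a subject who was randomized to placebo group accidentally received one or more doses of the active treatment during the study". Section 4.2.5 promises a listing of these subjects. Appendix 6.2 rates "Incorrect cohort IP dispensed to subject" as Major.

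On AD medication, Appendix 6.2 rates "Change in AD medications during course of the study" as Minor, and "use of AD medications at doses that have not been stable for at least 8 weeks prior to Screening V1" as Major. Only the first has a counterpart in the per-protocol list.

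**The concern.** A per-protocol analysis is normally read as the effect in eligible subjects who took what they were assigned. The set defined here secures a number of infusions but not that they came from the right arm. If per-protocol and ITT results agree, a reader may take this as reassurance about treatment errors, but both analyses keep the same affected subjects in the same arms.

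The AD-medication condition is uneven. Its evident purpose is to keep symptomatic drug changes from mixing with the study effect. It does this after the first dose but not for a change shortly before screening.

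**Working it through.** **1. Apply the definition to four cases.** Assume each subject meets the three listed inclusion criteria and had at least 14 infusions.

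| Case | Per-protocol? | Arm in the efficacy analysis |
|---|---|---|
| Placebo subject with one or more active doses | Yes | Placebo (low or high dose for safety) |
| Subject given the wrong cohort's product | Yes | As randomized |
| AD drug dose changed two weeks before Screening V1, then unchanged | Yes | As randomized |
| AD drug dose changed at Week 70 | No | – |

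**2. Check whether another part of the SAP closes the gap.**
- Section 4.2.4 uses the major and minor classes for summaries and listings only. It does not link them to the per-protocol set.
- The censoring analysis (4.3.2.3.1) covers treatment discontinuation and AD-medication change, not treatment errors or instability at entry.
- The model covariate is AD symptomatic medication use at baseline, yes or no (4.3.2.1, defined in 4.2.3). A recently changed regimen and a long-stable one are both coded yes.

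No planned efficacy analysis removes subjects who received the wrong treatment.

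**3. Size, for placebo subjects given active drug.** Section 3 supplies the inputs: difference 0.5, SD 1.92, 450 per group, 30% drop-out, two-sided 0.05.

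The plan's own figure first:
- Evaluable per group: 450 × 0.70 = 315.
- SE of the difference: 1.92 × √(2/315) = 0.153.
- Power: Φ(0.5/0.153 − 1.96) = Φ(1.31) ≈ 0.905, in line with the stated 90%.

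Now let a share p of per-protocol placebo subjects have the full treatment effect. The SAP gives no value for p, so 2% and 5% are assumptions. The contrast becomes 0.5 × (1 − p):
- p = 2%: 0.490, a shift of 0.010, or 0.010/0.153 ≈ 0.07 SE.
- p = 5%: 0.475, a shift of 0.025, or 0.025/0.153 ≈ 0.16 SE.

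For a given p this is an upper bound, because the Table 5 rule is triggered by a single active dose out of 20 infusions and one dose need not give the full effect. The per-protocol set cannot have more Week 78 observations than ITT, so on these inputs its SE is no smaller.

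Wrong-cohort product in the active arms and unstable entry medication cannot be sized from the SAP. For the former, the direction depends on which product was given.

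**The case against.** **The deviation classes do not contradict the list.** A reader might infer an inconsistency because a Minor deviation removes a subject while Major ones do not. The SAP does not support that. The classes serve reporting and do not rank relevance to efficacy: account sharing and consent-signature defects are also Major. On-study AD-medication change is excluded because sections 4.3.1, 4.3.2.1 and 4.3.2.3.1 treat it as an intercurrent event. Nor does the set keep every Major deviation, since ineligible CDR, MMSE or RBANS scores do remove a subject. This objection stands in full.

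**Disallowed therapy.** Appendix 6.2 rates "Administration of any disallowed concomitant therapy to the subject" as Major, and a reader might infer that it distorts efficacy. The SAP does not say which therapies are disallowed or why, so this is not shown. A blanket exclusion could remove subjects for reasons unrelated to outcome.

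**Entry instability arises before randomization.** It is balanced between arms in expectation, so a biased contrast does not follow. This stands; what remains is the uneven handling of one concern.

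**The stakes are low.** The analysis is supplementary and outside the testing sequence in 4.3.1, dilution from placebo crossover is toward the null, and both major deviations and affected placebo subjects are reported. This sets the severity. It does not supply the missing rule on treatment received.

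**Conclusion.** The point holds as a minor one. Followed as written, the per-protocol set can include subjects who did not receive their assigned treatment, analysed as though they had. The supplementary MMRM for CDR-SB and the three secondary endpoints therefore does not estimate the effect in subjects treated as assigned, and its agreement with ITT says nothing about robustness to treatment errors. Keeping subjects with unstable AD medication at entry, while removing those who change it later, is a lesser unevenness in the same list.

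A reader might go further and infer that the trial's efficacy conclusion is at risk. The document does not support that. As-randomized grouping is right for the primary ITT analysis, which is unaffected. The shift from placebo crossover is probably small: at most 0.025 points, about 0.16 SE, under the assumed 5% share with full effect. The SAP gives no counts, so the case rests on the definition and not on a demonstrated bias.

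**What to change.** Before unblinding, add to section 4.1.1 that the per-protocol population excludes:

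- Subjects who received study drug of the wrong treatment group: placebo subjects with any active dose, or subjects to whom incorrect cohort product was administered. Fix the rule while blinded, but apply it by program from the dosing records after unblinding, because it cannot be evaluated without the allocation. In the active arms, read the dosing records together with the deviation log, since titration and ARIA dose adjustments also change the dose level.
- Subjects whose AD symptomatic medication was not stable for 8 weeks before Screening V1. Identify them from medication dates and not from the deviation category alone, because that row also covers other chronic medications. This assumes that the recorded dates show dose changes before screening.

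Exclude a subject for disallowed therapy only where blinded review judges that the therapy affects cognition or function. If the sponsor prefers to keep any of these subjects, 4.1.1 should say why.

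The cost is a few lines of SAP text and programming, a limited blinded review, and a few more subjects leaving a supplementary analysis.
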